8.3. Adverse Events and Deaths

8.3.1. Adverse Event Dictionary

Clinical and laboratory adverse events (AEs) will be coded using the current version of Medical Dictionary for Regulatory Activities (MedDRA). SOC, high-level group term (HLGT), high level term (HLT), PT, and lowest-level term (LLT) will be provided in the AE dataset.

8.3.2. Adverse Event Severity

Adverse events are graded by the investigator as Grade 1 (mild), Grade 2 (moderate), Grade 3 (severe), or Grade 4 (life threatening) according to toxicity criteria specified in the study protocol. The severity grade of events for which the investigator did not record severity will be left as “missing” for data listings.

8.3.3. Relationship of Adverse Events to Study Drug

Related AEs are those for which the investigator selected “Related” on the AE eCRF to the question of “Related to Study Treatment”. Events for which the investigator did not record relationship to study drug will be considered related to study drug for summary purposes. However, by-subject data listings will show the relationship as missing.

8.3.4. Serious Adverse Events

Serious adverse events (SAEs) will be identified and captured as SAEs if AEs meet the definition of SAE specified in the study protocol. Serious adverse events captured and stored in the clinical database will be reconciled with the SAE database from the Gilead Pharmacovigilance & Epidemiology Department before data finalization.

8.3.5. Treatment-Emergent Adverse Events

8.3.5.1. Definition of Treatment-Emergent Adverse Events

E/C/F/TAF phase treatment-emergent AEs are defined as 1 or both of the following:

- Any AEs with an onset date on or after the E/C/F/TAF study drug start date and no later than 30 days after permanent discontinuation of the E/C/F/TAF study drug for subjects who do not participate in the B/F/TAF OL extension phase or the day prior to the date of the first B/F/TAF study drug dose for subjects who participate in the B/F/TAF OL extension phase, or
- Any AEs leading to premature discontinuation of E/C/F/TAF study drug.

B/F/TAF OL extension phase treatment-emergent AEs are defined as 1 or both of the following:

- Any AEs with an onset date on or after the B/F/TAF study drug start date and no later than 30 days after permanent discontinuation of the B/F/TAF study drug, or
- Any AEs leading to premature discontinuation of B/F/TAF study drug.

8.3.5.2. Incomplete Dates

If the onset date of the AE is incomplete and the AE stop date is not prior to the first dose date of E/C/F/TAF study drug, then the month and year (or year alone if month is not recorded) of onset determine whether an AE is treatment emergent.

The event is considered treatment emergent for the E/C/F/TAF phase if both of the following 2 criteria are met:

- The month and year (or year) of the AE onset is **the same as or after** the month and year (or year) of the first dose date of E/C/F/TAF study drug, and
- The month and year (or year) of the AE onset is **the same as or before** the month and year (or year) of the date corresponding to the minimum of (1) the last dose of E/C/F/TAF study drug plus 30 days AND (2) the first dose of B/F/TAF study drug minus 1 day

The event is considered treatment emergent for the B/F/TAF OL extension phase if both of the following 2 criteria are met:

- The month and year (or year) of the AE onset is **after** the month and year (or year) of the first dose date of B/F/TAF study drug, and
- The month and year (or year) of the AE onset is **the same as or before** the month and year (or year) of the date corresponding to 30 days after the date of last dose of B/F/TAF study drug

An AE with completely missing onset and stop dates, or with the onset date missing and a stop date on or after the first dose date of E/C/F/TAF study drug, will be considered to be treatment emergent for the E/C/F/TAF phase. In addition, an AE with the onset date missing and incomplete stop date with the same or later month and year (or year alone if month is not recorded) as the first dose date of E/C/F/TAF study drug will be considered treatment emergent.

8.3.6. Summaries of Adverse Events and Deaths

The number and percentage of subjects who experienced at least 1 TEAE will be provided and summarized by SOC, HLT, and PT separately for the E/C/F/TAF Safety Analysis Set and B/F/TAF Safety Analysis Set. For other AEs described below, summaries will be provided by SOC and PT separately for the E/C/F/TAF Safety Analysis Set and B/F/TAF Safety Analysis Set:

- Any Grade 2, 3, or 4 treatment-emergent AE
- Any Grade 3 or 4 treatment-emergent AE
- All treatment-emergent study-drug-related AEs
- Any Grade 2, 3, or 4 treatment-emergent study-drug-related AE
- Any Grade 3 or 4 treatment-emergent study-drug-related AE
- All treatment-emergent SAEs
- All treatment-emergent study-drug-related SAEs
- All treatment-emergent AEs that caused premature discontinuation from study drug

A brief, high-level summary of AEs described above will be provided by the number and percentage of subjects who experienced the above AEs. Treatment-emergent deaths observed in the study will also be included in this summary.

For the E/C/F/TAF Safety Analysis Set summary, treatment-emergent death refers to a death that occurred between the first E/C/F/TAF dose date and the last E/C/F/TAF dose date plus 30 days (inclusive) for subjects who do not participate in the B/F/TAF OL extension phase or the day prior to the date of the first B/F/TAF study drug dose for subjects who participate in the B/F/TAF OL extension phase.

For the B/F/TAF Safety Analysis Set summary, treatment-emergent death refers to a death that occurred between the first B/F/TAF dose date and the last B/F/TAF dose date plus 30 days (inclusive).

Multiple events will be counted only once per subject in each summary. Adverse events will be summarized and listed first in alphabetical order of SOC and HLT within each SOC (if applicable), and then by PT in descending order of total frequency within each SOC. For summaries by severity grade, the most severe grade will be used for those AEs that occurred more than once in an individual subject during the study.

In addition to the above summary tables, all treatment-emergent AEs will be summarized by PT only, in descending order of total frequency.

In addition, data listings will be provided for the following:

- All AEs (with a variable indicating whether the event is treatment-emergent)
- Grade 3 and 4 AEs
- Study-drug-related AEs
- SAEs
- Study-drug-related SAEs
- Deaths reported
- AEs leading to premature discontinuation of study drug.

8.3.7. Additional Analysis of Adverse Events

8.3.7.1. Stage 3 Opportunistic Illnesses in HIV

On an ongoing basis, AEs will be reviewed for events that might meet the definition of stage 3 opportunistic illnesses in HIV that are indicative of an AIDS-defining diagnosis (see Protocol Appendix 8). The Gilead medical monitor will review the possible stage 3 opportunistic illnesses and approve the events that meet the definition. Events that meet the stage 3 opportunistic illnesses definition diagnosis will be listed for all enrolled subjects.

8.3.7.2. Common Adverse Events Included in the FTC Prescribing Information

The common treatment-emergent AEs in the FTC Prescribing Information will be summarized by PT, in descending order of total frequency. The associated PTs are the following:

- Headache
- Diarrhea
- Nausea
- Fatigue
- Dizziness
- Depression
- Insomnia
- Abnormal dreams
- Rash
- Abdominal pain
- Asthenia
- Cough
- Rhinitis.

A by-subject listing will be provided for AEs with PT terms above for all enrolled subjects.

8.3.7.3. Cardiovascular or Cerebrovascular Events

Preferred terms for cardiovascular or cerebrovascular events are from relevant Standardised MedDRA Query (SMQ). The selected PT listing was provided by Gilead PVE and reviewed by Gilead medical monitors (see details in [Appendix 4](#)).

A data listing of cardiovascular or cerebrovascular events will be provided for the B/F/TAF Safety Analysis Set.

8.3.7.4. Hepatic Events

Preferred terms for hepatic events are from 15 relevant SMQs, which are identified as non-infectious and non-congenital hepatobiliary disorders. The selected PT listing was provided by Gilead PVE and reviewed by Gilead medical monitors (see details in [Appendix 5](#)).

A data listing of hepatic events will be provided for the B/F/TAF Safety Analysis Set.

8.4. Laboratory Evaluations

Laboratory data collected during the study will be analyzed and summarized using both quantitative and qualitative methods. Summaries of laboratory data will be provided for the E/C/F/TAF Safety Analysis Set and B/F/TAF Safety Analysis Set. The analysis will be based on values reported in conventional units. When values are below the lower limit of quantitation they will be listed as such, and the imputed value will be used for the purpose of calculating summary statistics as specified in Section 3.7.

A by-subject listing for laboratory test results will be provided by subject ID number and visit in chronological order for hematology and serum chemistry separately. Values falling outside of the reference range and/or having a severity grade of 1 or higher on the Gilead Grading Scale for Severity of Adverse Events and Laboratory Abnormalities will be flagged in the data listings, as appropriate.

8.4.1. Summaries of Numeric Laboratory Results

Descriptive statistics will be provided for each laboratory test specified in the study protocol as follows:

- Baseline value
- Value at each postbaseline analysis window
- Change from baseline at each postbaseline analysis window

In addition, percentage change from baseline at each postbaseline analysis window will also be provided for biomarker PTH.

A baseline laboratory value for the E/C/F/TAF phase will be defined as the last nonmissing value obtained on or prior to the date of first dose of E/C/F/TAF study drug. A baseline laboratory value for the B/F/TAF OL phase will be defined as the last nonmissing value obtained on or prior to the date of first dose of B/F/TAF study drug. Change from baseline to a postbaseline visit will be defined as the postbaseline value minus the baseline value. The mean, median, Q1, Q3, minimum, and maximum values will be displayed to the reported number of digits; SD values will be displayed to the reported number of digits plus 1.

In the case of multiple values in an analysis window, data will be selected for analysis as described in Section 3.8.3.

Calcium Corrected for Albumin

Calcium corrected for albumin will be calculated and summarized. The following formula will be used when both serum calcium and albumin results for a given blood draw are available and serum albumin value is < 4.0 g/dL.

- Calcium corrected for albumin (mg/dL) = serum calcium (mg/dL) + 0.8 × (4.0 - albumin (g/dL)).

Toxicity grading for calcium will be applied based on the corrected values.

Estimated GFR

The following formula will be used to calculate eGFR_{CG}:

- eGFR_{CG} (mL/min) = $[(140 - \text{age(yrs)}) \times \text{weight (kg)} \times (0.85 \text{ if female})] / (\text{SCr (mg/dL)} \times 72)$, where weight is total body mass in kilograms, and SCr is serum creatinine.

8.4.2. Graded Laboratory Values

The Gilead Grading Scale for Severity of Adverse Events and Laboratory Abnormalities will be used for assigning toxicity grade (0 to 4) to laboratory results for analysis. Grade 0 includes all values that do not meet the criteria for an abnormality of at least Grade 1. For laboratory tests with criteria for both increased and decreased levels, analyses for each direction (ie, increased, decreased) will be presented separately.

If there is any laboratory toxicity grading scale overlapping with normal reference ranges (eg, Grade 1 scale overlaps with normal reference range), laboratory values within normal range will be Grade 0 except for lipid tests.

For triglycerides, LDL, and cholesterol, the protocol-specified toxicity grade scale is for fasting test values, so nonfasting lipid results (or lipid results without known fasting status) will not be graded or summarized by toxicity grades.

For international normalized ratio (INR) of prothrombin time, protocol-specified toxicity grade scale depends on the upper limit of normal range (ULN). While the ULN of INR depends on whether a subject is taking anticoagulant medication or not (ie, Not taking oral anticoagulant: 0.8 - 1.2; Taking oral anticoagulant: 2.0 - 3.0), the information is not collected in Covance lab. As a result, INR will be graded by assuming the subject is not taking oral anticoagulant, which is a more conservative approach and may lead to over-reporting abnormalities for INR. Since INR and prothrombin time are reflex tests; only an absolute value and not the toxicity grade is needed for patient management purposes; most importantly, the toxicity grades for INR may be over-reported. INR and prothrombin time will not be included in the laboratory abnormalities summary tables but will be included in a listing.

8.4.2.1. Treatment-Emergent Laboratory Abnormalities

E/C/F/TAF treatment-emergent laboratory abnormalities are defined as values that increase at least 1 toxicity grade from baseline at any postbaseline time point up to 30 days after the permanent discontinuation of E/C/F/TAF study drug for subjects who do not participate in the B/F/TAF OL extension phase or up to the date of the first B/F/TAF study drug dose for subjects who participate in the B/F/TAF OL extension phase.

B/F/TAF treatment-emergent laboratory abnormalities are defined as values that increase at least 1 toxicity grade from baseline at any postbaseline time point up to 30 days after the permanent discontinuation of B/F/TAF study drug.

If the relevant baseline laboratory value is missing, any abnormality of at least Grade 1 observed within the time frame specified above will be considered treatment-emergent.

Fasting glucose and nonfasting glucose (including glucose result without a known fasting status) are graded based on different grading scales as specified in the protocol. Treatment-emergent laboratory abnormalities will be summarized for fasting glucose. Maximum postbaseline grade, instead of treatment-emergent grade, for nonfasting glucose will be summarized, as nonfasting glucose was not assessed at baseline visit for most of the subjects; therefore, whether an abnormality is treatment-emergent or not cannot be determined for these subjects.

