6.2. Pretreatment Assessments

6.2.1. Screening Visit

Subjects will be screened within 30 days before Day 1 Visit to determine eligibility for participation in the study. The following will be performed and documented at screening:

- Obtain written informed consent
- Obtain medical history including history of HIV-1 disease-related events, substance use, family history of cardiovascular disease (i.e. myocardial infarction, stroke, peripheral vascular/arterial disease, and/or angina) and prior medications within 30 days of the Screening Visit
- Complete physical examination (urogenital/anorectal exams will be performed at the discretion of the Investigator)
- Vital signs measurement (blood pressure, pulse, respiration rate and temperature) and weight
- 12-lead ECG performed supine
- Height
- Blood sample collection for the following laboratory analyses:
 - Serum pregnancy test (females of childbearing potential only). If the test is positive, the subject will not be enrolled.
 - FSH test is required for female subjects who have stopped menstruating for > 12 months but do not have documentation of ovarian hormonal failure.

- Chemistry profile: alkaline phosphatase, AST, ALT, GGT, total bilirubin, direct and indirect bilirubin, total protein, albumin, LDH, CPK, bicarbonate, BUN, calcium, chloride, creatinine, glucose, phosphorus, magnesium, potassium, sodium, uric acid, PT/INR, amylase (reflex lipase testing is performed in subjects with total amylase $> 1.5 \times \text{ULN}$) and parathyroid hormone (PTH)
 - Sample should be drawn prior to hemodialysis
 - Timing of draw and timing of hemodialysis should be recorded
- Estimated GFR according to the Cockcroft-Gault formula for creatinine clearance:

Male:
$$\frac{(140 - \text{age in years}) \times (\text{wt in kg})}{72 \times (\text{serum creatinine in mg/dL})} = \text{CL}_{\text{cr}} \text{ (mL/min)}$$

Female:
$$\frac{(140 - \text{age in years}) \times (\text{wt in kg}) \times 0.85}{72 \times (\text{serum creatinine in mg/dL})} = \text{CL}_{\text{cr}} \text{ (mL/min)}$$
- Hematology profile: complete blood count (CBC) with differential and platelet count
- CD4+ T cell count
- Plasma HIV-1 RNA (Taqman v2.0)
- Hepatitis B virus surface antigen serology (HBsAg)
- Hepatitis C virus (HCVAb) serology. If the antibody test result is positive, HCV RNA test will be performed to confirm HCV viremia.

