8.5.3. Laboratory Evaluations

Selected laboratory data will be summarized using only observed data. Absolute values and changes from baseline at all scheduled time points will be summarized.

Graded laboratory abnormalities will be defined using the GSI Grading Scale for severity of Adverse Events and Laboratory Abnormalities ([Appendix 6](#)).

Incidence of treatment-emergent laboratory abnormalities, defined as values that increase at least one toxicity grade from baseline at any time post baseline up to the date of last dose of study drug plus 30 days, will be summarized. If baseline data are missing, then any graded abnormality (i.e., at least a Grade 1) will be considered treatment-emergent. The maximum toxicity grade will be summarized by laboratory parameter.

Laboratory abnormalities that occur before the first dose of study drug or after the subject has been discontinued from treatment plus 30 days will be included in a data listing.

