8.4.2.2. Summaries of Laboratory Abnormalities

The following summaries (number and percentage of subjects) for treatment-emergent laboratory abnormalities will be provided by lab test; subjects will be categorized according to most severe postbaseline abnormality grade for a given lab test:

- Treatment-emergent laboratory abnormalities
- Treatment-emergent Grade 3 or 4 laboratory abnormalities

For all summaries of E/C/F/TAF laboratory abnormalities, the denominator is the number of subjects with any nonmissing postbaseline values up to 30 days after the last E/C/F/TAF dose date for subjects who do not participate in the B/F/TAF OL extension phase or up to the date of the first B/F/TAF study drug dose for subjects who participate in the B/F/TAF OL extension phase.

For all summaries of B/F/TAF laboratory abnormalities, the denominator is the number of subjects with any nonmissing postbaseline values up to 30 days after the last B/F/TAF dose date.

By-subject listings of treatment-emergent graded abnormalities and Grade 3 or 4 laboratory abnormalities will be provided by subject ID number and visit in chronological order.

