End date is completely missing

The event is treatment emergent for the B/F/TAF OL extension phase if the following 3 criteria are met:

- The month and year (or year) of onset date is after the month and year (or year) of the first dose of B/F/TAF study drug, and
- The month and year (or year) of the onset date is the same as or before the month and year (or year) of the date corresponding to the last dose of B/F/TAF study drug plus 30 days, and
- End date is as follows:

The (complete) end date is on or after the first B/F/TAF dose date, or

The month and year (or year) of end date is the same or after the month and year (or year) of the first dose of B/F/TAF study drug, or

End date is completely missing

Events with Completely Missing Onset Date

An AE with a completely missing onset date is defined as TEAE for the E/C/F/TAF phase if end date is as follows:

- The (complete) end date is on or after the first E/C/F/TAF dose date, or
- The month and year (or year) of end date is the same or after the month and year (or year) of the first dose of E/C/F/TAF study drug, or
- End date is completely missing

18) Calculation of ratios

To calculate laboratory ratios (eg, fasting total cholesterol to HDL ratio), lab value of each test in the ratio needs to be from the same accession number; if any test value used for the ratio calculation from the same accession number is missing, the ratio is not calculable (ie, missing).

19) Graded Laboratory Abnormalities Summary

The following labels will be used for treatment-emergent laboratory abnormalities and treatment-emergent Grade 3 or 4 laboratory abnormalities summary tables and listings:

Battery	Lab Test Label Used in l-labtox Listing	Toxicity Direction	Lab Test Label Used in t-labtox Table
Hematology	Hemoglobin	Decrease	Hemoglobin (Decreased)
	Neutrophils	Decrease	Neutrophils (Decreased)
	Platelets	Decrease	Platelets (Decreased)
	WBC	Decrease	WBC (Decreased)
Chemistry	Albumin	Decrease	Albumin (Decreased)
	Alkaline Phosphatase	Increase	Alkaline Phosphatase (Increased)
	ALT	Increase	ALT (Increased)
	Amylase	Increase	Amylase (Increased)
	AST	Increase	AST (Increased)
	Bicarbonate	Decrease	Bicarbonate (Decreased)
	Corrected Calcium	Increase	Corrected Calcium (Hypercalcemia)
	Corrected Calcium	Decrease	Corrected Calcium (Hypocalcemia)
	Creatine Kinase (CK)	Increase	Creatine Kinase (Increased)
	Creatinine	Increase	Creatinine (Increased)
	GGT	Increase	GGT (Increased)
	Lipase	Increase	Lipase (Increased)

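### Lipase is tested only when amylase exceeds 1.5 × ULN, so the missing-baseline rule may report pre-existing lipase elevations as new in the lipase row of the treatment-emergent laboratory tables

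*SAP*

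**What the plan says.** **When lipase is measured.** In the chemistry profile at Screening (protocol 6.2.1), "reflex lipase testing is performed in subjects with total amylase" above 1.5 × ULN. The same condition is attached at Day 1 (6.2.2), Weeks 2 to 96 (6.3) and the open-label extension (6.4.3). No visit draws lipase unconditionally.

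**What happens without a baseline.** SAP 8.4.2.1: "If the relevant baseline laboratory value is missing, any abnormality of at least Grade 1 observed within the time frame specified above" is classed as treatment-emergent. Protocol 8.5.3 has the same rule: "If baseline data are missing, then any graded abnormality (i.e., at least a Grade 1) will be considered treatment-emergent".

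**Where lipase is reported.** SAP Appendix 7, item 19, opens its list of tests with "The following labels will be used for treatment-emergent laboratory abnormalities and treatment-emergent Grade 3 or 4 laboratory abnormalities summary tables and listings". Increased lipase is on that list.

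**How a similar gap is handled.** For nonfasting glucose, SAP 8.4.2.1 substitutes the maximum postbaseline grade, "as nonfasting glucose was not assessed at baseline visit for most of the subjects", and accepts that emergence cannot then be established for those subjects. Lipase has no such exception.

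**Denominator.** SAP 8.4.2.2: "the denominator is the number of subjects with any nonmissing postbaseline values", within the phase-specific time limits.

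**The concern.** A missing-baseline rule that leans towards reporting is reasonable when baselines are lost sporadically. Here the baseline is absent by design, and the postbaseline test is triggered by a high value of a related enzyme. The first lipase result may simply mark the day amylase crossed the cut-off.

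Three features of the plan make this plausible:

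- The Week 48 interim summary in protocol 1.2.5 describes raised median amylase after baseline as characteristic of ESRD, so some subjects may sit near the trigger.
- Inclusion criterion 12 does not exclude raised lipase. It admits amylase up to 5 × ULN with no lipase limit, and higher amylase if lipase is no more than 5 × ULN.
- There are two scheduled pre-dose draws but eleven from Week 2 to Week 96, and SAP Appendix 7, item 14, counts every graded postbaseline result. Chance variation in amylase alone gives more opportunities for a first lipase after dosing than before it.

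At stake is how the lipase row is read. There is no control arm to reveal how much of it comes from the testing rule.

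**Working it through.** The documents give no lipase figure to reproduce, so the check is to apply the rules in order and then bound the size under stated assumptions.

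**1. The chain for one subject (hypothetical values).** Lipase grades in protocol Appendix 6: Grade 1 is above 1.0 to 1.5 × ULN; Grade 2 is above 1.5 to 3.0 × ULN.

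- Screening and Day 1 amylase 1.4 × ULN: no reflex, so no baseline lipase. True lipase is 1.6 × ULN, unmeasured.
- Week 24 amylase 1.6 × ULN: reflex lipase is run and reads 1.6 × ULN, Grade 2.
- Baseline is missing, so this is reported as a treatment-emergent Grade 2 lipase increase, although lipase has not moved.

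**2. Who is not affected.** SAP 8.4.1 takes baseline as the last nonmissing value on or before the first dose. A reflex lipase from Screening or Day 1 qualifies, and those subjects follow the ordinary one-grade rule. For B/F/TAF the reference point is the first B/F/TAF dose, so a reflex lipase from the E/C/F/TAF phase can serve as baseline, though it may be old.

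**3. Effect on an overall any-grade count.** Total amylase is Grade 1 at above 1.0 to 1.5 × ULN and Grade 2 at above 1.5 to 2.0 × ULN.

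- No baseline lipase means pre-dose amylase ≤ 1.5 × ULN: Grade 0 or 1.
- A reflex lipase on treatment means amylase > 1.5 × ULN: Grade 2 or higher.
- The subject has therefore risen at least one amylase grade and is already treatment-emergent for amylase. Lipase adds nobody to an any-grade count. It could only raise a subject's worst grade.

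**4. Size in the E/C/F/TAF phase.** N = 55 treated (mock disposition table in SAP Appendix 6). The documents do not give the other inputs, so these are assumptions:

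- a = share with pre-dose amylase above 1.5 × ULN, 0.1 to 0.3
- b = share of the rest who first cross it on treatment, 0.1 to 0.4
- q = share of those whose lipase was already graded before dosing, 0.2 to 0.5

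Pre-existing elevations counted as new = N × (1 − a) × b × q.

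| | a, b, q | First tested after dosing, N(1 − a)b | Counted as new | Of 55 |
|---|---|---|---|---|
| Low | 0.3, 0.1, 0.2 | 55 × 0.7 × 0.1 = 3.85 | 3.85 × 0.2 = 0.77 | 1.4% |
| High | 0.1, 0.4, 0.5 | 55 × 0.9 × 0.4 = 19.8 | 19.8 × 0.5 = 9.9 | 18.0% |

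If the denominator is only subjects with a postbaseline lipase, and everyone triggered before dosing is triggered again later, it is Na + N(1 − a)b. Low: 0.77 / (16.5 + 3.85) = 3.8%. High: 9.9 / (5.5 + 19.8) = 39.1%. If the treatment-emergent label requires a pre-dose lipase, the count is 0 throughout.

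**The case against.** The best defence is that the rule is prespecified in the protocol, errs towards reporting, and affects one row of a descriptive table in a study without formal testing. Without a baseline, new and old elevations cannot be separated, so relabelling would also take genuinely new elevations out of the treatment-emergent row, in subjects whose amylase did rise. By-subject listings let a reader check each case. All of this is correct. It limits the importance of the point, but it does not show that the label is right for a value whose emergence cannot be known.

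A reader might also infer more than the documents support:

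- *That overall abnormality counts are inflated.* Step 3 rules this out for any-grade counts. SAP 8.4.2.2 specifies summaries by test, with no overall row. A Grade 3 or 4 lipase could add a subject to an overall Grade 3 or 4 count if one were produced.
- *That the SAP's exclusion of INR and prothrombin time sets a precedent.* SAP 8.4.2 mentions their reflex status, but the main ground is that grades may be over-reported because anticoagulant use is not collected by the laboratory. INR is drawn at Screening, so baseline was not the issue. Only nonfasting glucose is a true parallel, and there the SAP says most subjects lacked a baseline; nothing shows that for lipase.
- *That the lipase percentage is taken over reflex-tested subjects only.* SAP 8.4.2.2 does not say whether its denominator is per test.
- *That raised amylase in ESRD makes the problem large.* It may do the opposite: if amylase was already above the cut-off at entry, more subjects have a baseline lipase. The interim summary reports no clinically relevant change in chemistry medians.

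**Conclusion.** The point holds, confined to the lipase row of the treatment-emergent and Grade 3 or 4 laboratory tables, mainly in the E/C/F/TAF phase. For subjects with no pre-dose reflex lipase, a pre-existing elevation may be reported as new, and nothing in the planned table separates it from a true rise.

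The number affected is unknown. The range of 1.4% to 18.0% of 55 rests wholly on assumed a, b and q, and it assumes the reflex rule was followed. The documents do not support saying that pre-existing lipase elevations in general are misreported, or that a particular percentage will be. The primary endpoint and the Week 96 Grade 3 or higher adverse event endpoint do not use this laboratory rule. This is a cheap improvement to one row, and it applies reasoning already in the same SAP section.

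**What to change.** - In SAP 8.4.2.1, extend the nonfasting-glucose approach to lipase: summarise maximum postbaseline grade, and call a value treatment-emergent only when the subject has a lipase result on or before the first dose of the relevant phase.
- Footnote the lipase row with the numbers reflex-tested before and after dosing and the denominator used.
- Record the departure from protocol 8.5.3 in SAP 8.10, which now states that none is planned. If the signed SAP is not reopened, SAP Section 1 already provides for documenting later changes in the final clinical study report.

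The cost is a sentence, a footnote and a declaration, with minor programming and no new data. The downside is that a truly new lipase rise without a baseline is shown as a maximum postbaseline grade rather than as treatment-emergent; its full grade remains visible.
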